Parents, PCPs, point people, and leaders will receive no direct benefits from participating in this study. Participants who enroll in this trial will benefit from the knowledge that they are contributing in an important way to potentially furthering scientific knowledge about reducing firearm access and related suicide risk. Both health systems included in our study indicated that they would adopt this approach if we can demonstrate its effectiveness in this trial, suggesting the sustainability of the proposed work. Furthermore, the evidence and insights generated can be taken to scale in the MHRN which includes 14 healthcare systems which are closely integrated. The knowledge gained on how to implement a program like *SAFE Firearm* could be applied to other pediatric primary care settings and implemented at other health systems.

Equity Supplement Benefits: Participants may find satisfaction in sharing their perspectives with our research team as their feedback will be used to inform our facilitation implementation strategy. Their feedback may help the research team better understand perspectives about the barriers to implementation. The ratio of risks to benefit is reasonable given the importance of the information to be gleaned by this research.

3. Subject Privacy:

Privacy will be given utmost consideration and is highly valued in the proposed research. No research activities involve any direct interaction with subjects that would pose risk to their privacy.

Equity Supplement Subject Privacy: Privacy will be given utmost consideration and is highly valued in the proposed research. Participants will complete the interview over the phone or by videoconferencing if the participant prefers, and so can elect where they take the phone call; the interview will be in a private location where no one can overhear the content.

4. Subject Confidentiality:

Confidentiality refers to the subject's understanding of, and agreement to, the ways in which identifiable information will be stored and shared.

How will confidentiality of data be maintained? Check all that apply.

- Paper-based records will be kept in a secure location and only be accessible to personnel involved in the study.
- Computer-based files will only be made available to personnel involved in the study through the use of access privileges and passwords.
- Prior to access to any study-related information, personnel will be required to sign statements agreeing to protect the security and confidentiality of identifiable information.
- Whenever feasible, identifiers will be removed from study-related information.
- A Certificate of Confidentiality will be obtained, because the research could place the subject at risk of criminal or civil liability or cause damage to the subject's financial standing, employability, or liability.
- A waiver of documentation of consent is being requested, because the only link between the subject and the study would be the consent document and the primary risk is a breach of confidentiality. (This is not an option for FDA-regulated research.)
- Precautions are in place to ensure the data is secure by using passwords and encryption, because the research involves web-based surveys.
- Audio and/or video recordings will be transcribed and then destroyed to eliminate audible identification of subjects.
- Other (specify):

To protect participant confidentiality, only the research team outlined in this application will have access to review identified research records. Confidentiality will be protected to the fullest extent allowable under the law. See the **Data Management** section for more details.

For data that needs to be transmitted, it will be done through a Penn-approved secure encrypted file transfer solution as is described in Penn IRB's Guidance on Electronic Data Protection Requirements for Research Involving the Use of PHI. Records will not be released without the participant's consent unless required by law (e.g., imminent risk of harm to self suspected) or court order. When results of the research are presented at scientific meetings or published, no identifying information will be included.

All identifiable data, including the master list linking identifiers to the ID number and recordings, will be destroyed in 2030, five years after the award period ends.

5. Protected Health Information

Full details regarding data sharing and data management regarding PHI and PII is outlined in the data sharing and management appendix.

6. Compensation:

- Parent surveys (Aims 1 and 3). Parent participants for Part 1 of the parent survey will not receive compensation. Parent participants for Part 2 will be eligible for an incentive (i.e., \$100 e-gift card) via lottery for survey completion.
- PCP surveys (Aims 1 and 2). If allowed by their respective system, PCP participants will receive \$20 e-gift cards or we will make an altruistic gift (\$20 donation to a suicide prevention charity on their behalf) each time they complete a survey.
- PCP, point people, and leader interviews (Aim 2). If allowed by their respective system, PCP, point people, and leader participants will receive a \$25 e-gift card or health system-branded gift of equivalent value for participating in an interview.
 - Equity supplement: Based on what is allowed at each health system, participants will receive a \$50 electronic gift card (or if no gift card is permitted for research study incentives by the health system, we will send a personalized thank you email).

7. Data and Safety Monitoring:

Diligent data and safety monitoring will be conducted by the PI and research team at Penn, Northwestern, HFH, and KPCO throughout the conduct of this study. This monitoring plan includes tracking participant safety and demographics, monitoring the safety of data, and monitoring and appropriately reporting adverse event activity. The PI and appropriate co-investigators will review data collected to ensure that no study findings warrant immediate intervention. We believe this research poses no greater than *minimal risk* and have proposed a monitoring plan that reflects this risk level.

The Northwestern PI ([name]) will be responsible for oversight of potential adverse events. An adverse event (AE) is any untoward medical occurrence in a subject during participation in the clinical study. We anticipate two potential types of AEs that could be directly related to study participation. These include distress experienced with regard to research participation and breach of confidentiality and privacy. With regard to the former, we have protocols in place that include conferring with the PI (who is a licensed clinical psychologist) or a staff psychologist. With regard to the latter, we have appropriate safeguards to reduce risk of breach of confidentiality and privacy. As we are not legally mandated by any child access prevention law to disclose or report firearm storage practices, we do not anticipate AEs related to participants sharing information about their firearm storage practices with our research team. Additionally, we will defer to the respective health systems' procedures and policies related to any suicidal thoughts and/or behaviors identified during the course of this project. We appreciate the sensitive topic of discussion, and are committed to taking the appropriate steps if any unanticipated problems are identified during the course of this project. Otherwise, any risks related to additional potential AEs are not expected because the program, implementation strategies, and assessments pose minimal risk to subjects.

All members of the research team who will be involved in the design and conduct of the study must receive education in human research subjects protection from a training program that is approved by a properly constituted independent Ethics Committee or Institutional Review Board. The PI will be responsible for ensuring project faculty and staff have the equipment and training required to protect privacy and confidentiality and will monitor and document that these individuals are properly certified. If new senior/key personnel and staff become involved in the research, documentation that they have received the required education will be included in the annual progress reports.

The Penn IRB will serve as the IRB of record for any external ethics review boards or IRBs applicable to researchers from other institutions who may have access to human research subjects identified data (i.e. HFH, KPCO, Northwestern).

DSMB. Additionally, we have convened a three-member DSMB from faculty outside of the four institutions involved in this project (Penn, Northwestern, HFH, KPCO). DSMB composition includes the following: (1) a health services researcher with expertise in health systems and collection of data through EHR, (2) a biostatistician with expertise in longitudinal analysis, field trials, and clinical trial data, (3) an implementation research expert and firearm researcher. The DSMB will be an independent group of experts charged with reviewing study data for data quality and integrity, adherence to the protocol, participant safety, and study conduct and progress. They will also make determinations regarding study continuations, modifications, and suspensions/terminations. DSMB members will be independent from any professional or financial conflict of interest with the research project and/or study investigators. The DSMB will meet at least once yearly via phone conference calls for the duration of the project.

The DSMB will elect a Chair to moderate the meetings. At the initial meeting, the DSMB will review and approve all study protocols before study initiation to ensure participant safety. Protocols will include formal procedures for reporting and tracking all adverse reactions to the NIH and IRBs; tracking progress in the study; and identifying any need for premature termination of the protocol. At subsequent meetings, the DSMB will be provided with summary study progress reports and adverse events. The DSMB will provide a summary report following each meeting. We will not require the DSMB to conduct interim analyses of data prior to the end of the study.

8. Investigator's Risk/Benefit Assessment:

This study presents minimal risk that is balanced by the potential benefits of the research to society. This assessment is consistent for the equity supplement.

INFORMED CONSENT:

1. Consent Process:

We are requesting a waiver of written documentation of consent (see below) from the Penn IRB for participants who agree to participate in the surveys (parents, PCPs) and/or interviews (PCPs, point people, leaders). Because surveys will be completed via REDCap or phone and interviews will be conducted remotely, we will not have an opportunity to collect a signed copy of the consent form. We will not collect signed consent forms from participants who complete the parent survey via mail; these participants will receive a consent form to review before completing the survey. In the consent form and the introductory letter that they receive in the mail with the survey, they will be instructed that their completion and returning of the survey will be considered their consent to participate in the research study.

For the REDCap, mailed, and phone surveys, the required elements of informed consent will be described to the participant and, if they agree to participate, participants will consent by agreeing and proceeding to the electronic survey, completing the survey and returning it to the research team by mail, or providing verbal consent for surveys completed over the phone. Only participants who agree will be able to proceed to the online/verbal survey.

Participants who complete the mailed survey will be explicitly instructed in both the mailed letter that accompanies the survey and the consent form that their completion of the survey is considered their consent. Additionally, the letter specifies that they should not complete the survey before reviewing the consent form and deciding to participate. For participants who complete the survey over the phone, a member of our research team will conduct informed consent remotely. We will review the required elements of informed consent and answer any questions the potential participant might have. Potential participants will be encouraged to ask questions about the project.

Participants will be provided with a copy of the IRB approved consent document for their records. If they agree to participate, the research team will document the consent process in REDCap.

For the interviews, a member of our research team will conduct informed consent remotely. We will review the required elements of informed consent and answer any questions the potential participant might have. Potential participants will be encouraged to ask questions about the project. Participants will be provided with a copy of the IRB approved consent document for their records. If they agree to participate, the interview team will document the consent process in REDCap.

All potential participants will be informed that participation is voluntary and provided with the information that they need to make an informed choice. We will provide contact information to all potential survey respondents in case they have any questions before, during, or after completing the survey. Potential interview participants will be asked if they have any questions and if they agree to participate before any research questions are asked. All participants will be informed that their decision to participate or not will not impact their relationship (i.e., services or employment) with their health system.

For the equity supplement, we are also requesting a waiver of written documentation of consent from the IRB for participants who agree to participate in the qualitative interview. Due to the Covid-19 pandemic and the geographic spread of participants (e.g., Colorado, Michigan), we have decided to conduct these interviews by phone or videoconference to minimize risk posed to participants and to our research team. Because these meetings will be conducted by phone or videoconference, we will not have an opportunity to collect a signed copy of the consent form. A member of our interview team will conduct informed consent for qualitative interview participants over the phone or videoconference. We will review the required elements of informed consent and answer any questions the

potential participant might have. Potential participants will be encouraged to ask questions about the project. Participants will be offered a copy of the IRB approved consent form for their records. If they agree to participate, the interview team will document the consent process in REDCap. All potential qualitative interview participants will be asked to confirm that they understand the information provided, understand that participation is voluntary, and feel able to make an informed choice. All participants will be assured during the informed consent process that their decision to participate or not will not impact their relationship (i.e., services or employment) with their health system.

2. Waiver of Informed Consent:

- **Waiver of Informed Consent.** The trial is pragmatic in nature, assessing the impact of implementation strategies (i.e. *Nudge* vs. *Nudge+*) delivered to PCPs through minor adjustments to existing workflow delivered through the EHR. Changes to workflow are by necessity systematically applied to all PCPs within the practices. Further, these changes to workflow are being implemented as part of leadership commitment to deploying the *SAFE Firearm* program and EHR Nudges and Facilitation with data collection to allow for evaluation (i.e., *SAFE Firearm* will be considered standard of practice). Because PCPs will still be free to engage with parents as they see fit and the implementation strategies represent minimal risk to PCPs and parents, we have requested a **waiver of informed consent** for allowing EHR/Administrative data to be collected for Aims 1 and 3. This approach will also aid implementation integrity and generalizability by avoiding behavior changes related to observation (i.e., the Hawthorne effect). The PI has worked closely with the Nudge Unit in the past on similar pragmatic trials that have received this waiver of informed consent, and our study team has designed the study with their trials in mind. As such, we believe there are several reasons to justify why a waiver of informed consent is requested (and has been granted for similar studies at Penn). First, it is not feasible to consent every provider and parent. Second, if consent was obtained from providers and parents, they would know they were being studied and this could change their behavior. This could potentially disrupt the design of the study and make interpretation of the findings challenging. Third, clinicians are not forced to implement the *SAFE Firearm* program (which, as a reminder, is an evidence-based practice that is being implemented in both health systems) and parents are not forced to engage in a conversation with their provider and they are not forced to take a cable lock. In all aims, providers can choose to use their best clinical judgement when it comes to the *SAFE Firearm* program. This research involves no more than minimal risk to the participants and will not adversely impact the rights and welfare of participants. As described above, the waiver is essential to research as this research could not be practicably carried out without this waiver.
- **Waiver of Documentation of Consent for Online/Mailed/Phone Surveys.** All surveys completed by parents (Aims 1 and 3) and PCPs (Aims 1 and 2) will be completed via phone, mail, or electronic platforms, and thus we are requesting waiver of written documentation of consent from the IRB. The required elements of informed consent will be described to the participant and, if they agree to participate, participants will consent by agreeing and proceeding to the electronic/phone survey. Mailed survey participants will be instructed to review the consent form before completing the survey. Only participants who agree will be able to proceed to the online/phone survey. Mailed survey participants will be instructed not to complete the survey until they have reviewed the consent form and decide to participate. For phone surveys, the required elements of consent will be described to the potential participant at the beginning of the survey, before any research questions are asked. If the participant verbally agrees to be complete the survey, the research staff who is conducting the interview will document the consent process. This research activity presents no more than minimal risk of harm to subjects and involves no procedures for which written consent is normally required outside of the research context.
- **Partial Waiver of Consent for Part 1 Parent Survey.** For the one-question Part 1 parent survey, we will share a link to the consent form in the introductory message sent before the survey question text message or in the survey invitation sent via email or patient portal message. All the required elements of consent will be described to the participant. In the informed consent form, they will be instructed to review the consent form before completing the survey. The consent form will also indicate that their completion of the survey indicates their consent to participate in the research. This research activity presents no more than minimal risk of harm to subjects and involves no procedures for which written consent is normally required outside of the research context.

- Waiver of Documentation of Consent for Interviews. All interviews will be completed remotely and audio-recorded. The required elements of consent will be described to the potential participant at the beginning of the interview, before any research questions are asked. If the interview participant verbally agrees to be interviewed, the research staff who is conducting the interview will document the consent process. This research activity presents no more than minimal risk of harm to subjects and involves no procedures for which written consent is normally required outside of the research context.
- For the equity supplement, we also request a waiver of written documentation of informed consent (as described above) for the qualitative interview since the research presents no more than minimal risk of harm to subjects and involves no procedures for which written consent is normally required outside of the research context. The required elements of informed consent will be described over the phone or videoconference before any study activities occur.

RESOURCES NECESSARY FOR HUMAN RESEARCH PROTECTION:

Adequate facilities are available at Penn, Northwestern, HFH, and KPCO. The members of the research team are outlined in the application and include the Penn and Northwestern PIs, research investigators, full time research staff, and part time undergraduate research assistants. The entire team will be overseen by the PIs ([name], [name]). All personnel will complete required training before being granted access to any identifying information. This includes training on confidentiality through the CITI course. All Penn personnel will also sign confidentiality statements. These confidentiality statements will specify the procedures for reporting unintentional breaches in confidentiality to the PIs. The confidentiality statements also specify that violations of participants' confidentiality, either unintentional or deliberate, may result in termination of hire. The PIs will conduct training with all research personnel regarding data, limits of confidentiality, maintaining confidentiality, and proper study procedures. Personnel from HFH, KPCO, and Northwestern sign similar confidentiality statements and undergo similar research training within their respective systems.

REFERENCES

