Prior to launching the full trial, we are piloting the delivery of the *SAFE Firearm* program in 2 clinics in each health system during an approximately 4-5 month period. Pilot procedures will mirror the procedures described in the protocol and use the same parent survey instrument. After the pilot, we will conduct this sub-study. Specifically, we will explore any signals of disparities and examine *SAFE Firearm* delivery by children's medical complexity (per ICD-9 and -10 codes), sex, and race/ethnicity. *SAFE Firearm* delivery will be captured by the post-visit parent survey described in this protocol (below; see Parent Surveys [Aims 1 and 3]), which will be confirming receipt of the program; consistent with the primary outcome measure for the ASPIRE trial (as described in this protocol), clinicians must report "yes" to both program components (i.e., counseling and cable lock offer) to have received the program. Medical complexity will be determined by ICD-9 and -10 codes in the EHR, and race/ethnicity also be from the EHR (as described in the Data Collection section of this protocol). We will fit two separate inverse probability weighted GEE logistic regression models to analyze the data. We will use a parameter of 10% difference in program delivery for youth in each group of interest to explore further. Regardless of whether we detect differences in program delivery, we will conduct qualitative interviews with up to 12 participants from Henry Ford Health or Kaiser Permanente Colorado to identify barriers to *SAFE Firearm* delivery. We will use the Health Equity

Implementation Framework (HEIF) as a theoretical framework for the interviews, analysis, and interpretation of findings. The HEIF is a multilevel framework that assesses health equity determinants to identify factors that promote or hinder implementation of new interventions. The HEIF is well-suited for this inquiry given its explicit attention to the clinical encounter in which the intervention is delivered and emphasis on facilitation as essential process to address implementation problems, specifically disparities. Following analysis of the interview data, the research team will identify strategies to optimize facilitation.

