As an extension of the Equity Supplement, we will repeat the above-described statistical analysis to descriptively evaluate approximately 6 months of data (i.e., from approximately March 2022-September 2022) in the same pilot clinics (N=4) to confirm the preliminary findings from the pre-trial pilot study. If we find a 10% difference in program delivery (as indicated above to signify clinical significance) by patients' race/ethnicity and sex, the trial facilitators (local members of the research team at Henry Ford and Kaiser CO) will feed back this information to pilot clinic clinicians, with the goal of increasing clinician awareness of potential disparities in implementation and broadly learning from this feedback process. If we do not find any clinically significant differences in program delivery, the facilitators will notify these clinics of the positive findings. These activities fall under the types of facilitation activities that the trial facilitators are already doing at clinics participating in the trial. For the Equity Supplement, we are simply proposing to do these same activities with the pilot clinics at both sites. We do not expect greater than minimal risks.

Study Duration:

We propose to conduct this project from 08/01/2020 through 06/30/2025, with human subject research activities starting no earlier than 01/01/2021 and data collection ending no later than 12/31/2024. After piloting procedures (planned for approximately April-May 2021 for parent survey pilot, and Fall 2021 and early 2022 [approximately October-February; duration of approximately 4-5 months] for SAFE Firearm program pilot), we plan to start in July 2021 to collect data across all aims during a 6-month pre-implementation period, a 1-year implementation period, and a 1-year sustainment period. We anticipate using the end of the project time to conduct analysis and prepare manuscripts.

Equity Supplement Study Duration:

S.A.F.E. Firearm piloting procedures will occur in Fall 2021 and early 2022 and last approximately 4-5 months. We propose to conduct interviews from January 2022-February 2022 (approximately 6 weeks). We will re-analyze approximately 6 months of pilot clinic data in approximately late October 2022 (once IRB approval is received) and engage in facilitation activities shortly afterward as described above.

METHODS:

1. Study Instruments:

- **Parent surveys (Aims 1 and 3).**

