- **Aim 3 Analysis.** We do not include a power analysis because in a hybrid type III effectiveness-implementation trial, power is based on implementation outcomes.⁶¹ We note that we will not be powered to detect reductions in

youth suicide attempts, deaths, and unintentional firearm injury and mortality given very low prevalence. However, we will conduct exploratory analyses using the same modeling techniques described in Aim 1 to assess the impact of the implementation conditions on parent-reported firearm storage behavior, youth suicide attempts, deaths, and unintentional firearm injury.

- **Equity supplement Analysis:** For analysis of the pilot data, we will fit two separate inverse probability weighted GEE logistic regression models to analyze the data. We will use a parameter of 10% difference in program delivery for youth in either group of interest to explore further. For analysis of the clinician interviews, we will use rapid qualitative analytic techniques, specifically structured summaries and matrix displays. We will begin analysis by systematically condensing the data (i.e., transcripts, field notes) to create an inventory of the most contextually meaningful data segments and quotations for each data collection episode. We will develop a structured template with key domains (i.e., clinical encounter, patient factors) to standardize the capture of interview content and increase the accessibility of the data. After all interviews are transformed onto structured templates, we will then transfer the summary points into a matrix, which will expedite recognition of similarities, differences, and trends across participants. We will use the matrix to develop barriers for program delivery. We will repeat the statistical analysis to descriptively evaluate approximately 6 months of data (i.e., from approximately March 2022-September 2022) in the same pilot clinics (N=4) to confirm the preliminary findings from the pre-trial pilot study.

RISK/BENEFIT ASSESSMENT:

1. Risks:

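### The equity extension sends pilot clinics a favourable message whenever no observed gap reaches 10%, with no account of uncertainty and no inconclusive outcome

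*Protocol*

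**What the plan says.** The Equity Supplement Study Design section first sets the trigger for the pilot data: "We will use a parameter of 10% difference in program delivery for youth in each group of interest to explore further". The Equity supplement Analysis paragraph under Statistical Analysis repeats it almost word for word: "We will use a parameter of 10% difference in program delivery for youth in either group of interest to explore further".

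The extension then takes the same four clinics and will "descriptively evaluate approximately 6 months of data", using the "inverse probability weighted GEE logistic regression models" already planned for the pilot. Two outcomes are provided for:

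- The first begins "If we find a 10% difference in program delivery (as indicated above to signify clinical significance". It applies to race/ethnicity and sex, and leads facilitators to feed the result back to clinicians.
- The second is "If we do not find any clinically significant differences in program delivery, the facilitators will notify these clinics of the positive findings".

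Neither section attaches an interval, a test, a precision requirement or a minimum group size to the 10%. Neither says whether 10% is absolute or relative, which race/ethnicity groups are contrasted, or how a logistic model result becomes a percentage difference. The source of the delivery measure is also unclear. The design section says it is captured by the post-visit parent survey, then in the same sentence makes delivery depend on what clinicians report.

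**The concern.** The rule turns not having seen a 10% gap into a favourable message to clinicians. Those are different statements. A small observed gap in a small subgroup is compatible with a large true one, and the plan has no branch for data that cannot tell. The protocol itself treats 10% as clinically significant, so the rule can reassure clinics about a disparity of the size the sub-study was built to notice. In the other direction, a gap that reaches 10% by chance in a small group is fed back without any indication of how uncertain it is.

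**Working it through.** The documents give no sample size, power or error rate for this extension, so there is no stated figure to reproduce.

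**Inputs from the documents**
- Threshold: 10%, read here as 10 percentage points (an assumption).
- 48,475 eligible patients a year and 41 clinics (protocol, Aim 1 Analysis); 30 clinics (protocol, Introduction and Purpose; SAP). The 48,475 counts parents/patients and is used as a stand-in for visits.
- 74,080 encounters a year (protocol, Target Population and Accrual), used as a sensitivity figure.
- Survey response rates tried: 10% to 37% (SAP amendments).
- Delivery of both components: 30.0% by survey, 45.3% by EHR (SAP amendments table).

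**Assumed:** four clinics of average size; subgroup shares as stated below; no clustering and no weight variance, both of which would mainly widen the standard error (SE).

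**Volume in 4 clinics over 6 months.** 48,475/41 × 4 × 0.5 ≈ 2,365; 48,475/30 × 4 × 0.5 ≈ 3,232. Survey responses run from 0.10 × 2,365 ≈ 236 to 0.37 × 3,232 ≈ 1,196.

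**1. One contrast.** P(no flag) ≈ Φ((10 − true gap)/SE). At a true gap of 10 this is Φ(0) = 0.50, whatever the sample size. Simulating counts in two equal groups gives 0.47 to 0.49, because ties at exactly 10 are flagged. Larger gaps are missed less often. At a true 15 points with equal groups:
- total N = 240: 0.20 to 0.22
- N = 500: 0.11 to 0.13
- N = 900: 0.05 to 0.07
- N ≥ 2,400: under 0.01

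**2. The notice.** It requires every contrast to stay below 10. Simulation used sex split equally and four race/ethnicity groups with assumed shares of 50/20/20/10%, each compared with the largest. With one true 10-point gap and the rest null, the probability of the favourable notice is:
- at 30.0% delivery: 0.20 to 0.23 (N = 240), 0.35 to 0.37 (N = 500), 0.44 to 0.45 (N = 900)
- at 45.3% delivery and N = 2,400 to 3,600: 0.49 to 0.50

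The lower survey values arise partly because chance flags in other groups block the notice. With no gap anywhere, N = 240 and 30.0% delivery, the notice goes out only 0.375 of the time. If sex and one race/ethnicity group both truly differ by 10 points, the notice probability is 0.11 to 0.25 across the sample sizes and both delivery levels.

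**3. Precision for a subgroup of share s = 0.10.** SE = √[p(1−p)(1/(ns) + 1/(n(1−s)))]; half-width = 1.96 × SE.
- Survey, n = 1,196: √[0.21 × (1/119.6 + 1/1,076.4)] = 0.0442, half-width 8.7 points.
- Survey, n = 236.5: SE 0.0993, half-width 19.5 points.
- EHR, n = 3,232: √[0.453 × 0.547 × (1/323.2 + 1/2,908.8)] = 0.0292, half-width 5.7 points.
- EHR, n = 2,365: SE 0.0341, half-width 6.7 points.
- Most favourable survey case, using encounters: 74,080/30 × 4 × 0.5 ≈ 4,939; × 0.37 ≈ 1,827; SE 0.0357, half-width 7.0 points.

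**4. Chance flags with no true gap.** 2 × (1 − Φ(0.10/SE)).
- EHR: 0.06% to 0.3% for a 10% subgroup; about 1% to 3% for a 5% subgroup.
- Survey (n = 236 to 1,196): about 2% to 31% for a 10% subgroup; about 10% to 46% for a 5% subgroup.

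**5. Interval rule.** If absence is claimed only when the whole 95% interval lies within ±10 points, a true 10-point gap in one contrast is called absent at most about 2.5% of the time (simulated 0.000 to 0.025), against 0.47 to 0.50 under the written rule.

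**6. Scale.** A relative 10% would be 0.10 × 45.3 ≈ 4.5 points, or 0.10 × 30.0 = 3.0 points. At 4.5 points, a true 10-point gap in one contrast goes unflagged about 0.3% (SE 0.020) to 20% (SE 0.064) of the time. A true gap equal to the threshold is still missed about half the time.

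**The case against.** A reader might infer that clinics with a 10-point disparity will be told good news half the time. The documents do not support that as a general statement. Half applies to one contrast with the truth exactly on the cut-off, which is a property of any cut-off on a symmetric estimate and says nothing special about this design. The notice needs all contrasts to pass, so half is its ceiling. The figure also presumes an absolute threshold, which the protocol does not state. This part of the objection stands and sets the limits of the point.

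It can also be said that the planned models yield standard errors, that the plan never says intervals will be withheld, and that the SAP (Primary outcome model) refers to pilot delivery differing significantly by sex and race, so the team did not look at size alone. That is fair. But the SAP sentence explains a covariate choice for the main trial. The extension's own rule names no quantity other than the 10% difference.

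Third, the alarming precision and chance-flag figures depend on the parent survey being the source. On EHR data an observed zero would exclude 10 points for a 10% subgroup, and chance flags are rare. This stands, and the protocol leaves the source ambiguous.

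Finally, the analysis is labelled descriptive, the clinician interviews go ahead whatever it shows, and the action is awareness-raising in four pilot clinics. That limits the consequence. It does not excuse the favourable message, because a descriptive estimate that prompts a statement to clinicians still needs its uncertainty attached.

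**Conclusion.** The point holds as a fault in the decision rule and its message. The plan relays absence of an observed 10% difference as favourable news, ignores uncertainty and has no inconclusive outcome. The chance that a true disparity at the threshold ends in that notice is at most about half, and lower at survey-sized samples. Whether the data could exclude a 10-point gap depends mainly on the source: doubtful or impossible for small subgroups on most survey scenarios, feasible for a 10% subgroup on EHR data. These sizes rest on an absolute reading of 10%, average-sized clinics, assumed subgroup shares and no clustering. If the trigger required both race/ethnicity and sex to differ, disparities would be missed more often.

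It would be wrong to infer that the randomised comparison is affected, or that chance flags are frequent whichever source is used. The consequence is confined to feedback to four pilot clinics. The change is worth making because it is cheap and goes to the sub-study's purpose.

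**What to change.** - State the threshold as 10 percentage points.
- Report every gap, flagged or not, with its 95% interval and group size, obtained from the planned GEE models.
- Describe a flag as a possible disparity, and note when its interval includes zero.
- Say *no disparity of 10 points or more* only when the whole interval lies within ±10 points.
- Otherwise replace the favourable message with *no difference of 10 points or more was observed, but the data cannot rule one out*.

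If notices have already been sent, the same intervals and wording should accompany any report of these results.

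The cost is protocol wording and intervals from models already planned. The downside is that some clinics receive an inconclusive message. The change removes most of the false reassurance. It does not make a true 10-point gap more likely to be flagged, nor chance flags in small groups less frequent; it makes their uncertainty visible.
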